12.3 PROCEDURES FOR HANDLING MISSING, UNUSED AND SPURIOUS DATA

No imputation of values for missing data will be performed. Standard clinical monitoring and data management practices will be used to ensure the integrity of the data

Interim analysis

Interim analyses will be conducted after last patient in dose Cohort 3 has completed 6-week follow up (Visit 8) and will be used to determine the progress of the study and dose decision for expansion Cohort 4. Further analysis will be conducted after each cohort has completed 12 and 24 weeks follow up (Visit 8 and 10).

13 MONITORING

13.1 MONITORING OF CASE REPORT FORMS

The study will be monitored by a CRO on behalf of the Sponsor. Monitoring will be conducted per ICH GCP guidelines and Sponsor SOPs. The Monitor will visit the Investigator at regular intervals to review the progress and conduct of the study. The CRFs will be checked for completeness and accuracy against the patient records, charts, laboratory reports, and scans. Anonymity of the patient will be maintained at all times.

13.2 SAFETY DATA MONITORING

The Study Steering Committee (SSC) will review and evaluate all toxicities causally associated with NOX66 treatment and or the radiation therapy combination therapy. The SSC will consist of:

- Principal Investigator from each clinical site, or medical designee
- Sponsor's Medical Monitor
- CRO Medical Representative (if applicable)
- Director of Clinical Development, Noxopharm Ltd

Review of any adverse events of Grade 2 toxicity and above, considered by the Principal Investigator to be related to idronoxil (NOX66), will be reported to the SSC immediately and decision on the continuation of the patient individually, and the study in general, will be provided.

The Study Steering Committee will review the Safety Data and determine dose cohort escalation following completion of treatment cycle (Visit 7) of final patient in a cohort.

The SSC will determine the dose for cohort expansion based on the review of accumulated safety data, on treatment response and disease evaluation following WEEK 6 assessments of all patients and determine continuation of the study.

13.3 AUDITING

Regulatory authorities, the HREC/EC or the Sponsor may request access to patient clinical notes and other relevant study documentation for an on-site audit or inspection at any time during or after study completion. The Investigator is obliged to facilitate this process by allowing full access.

14 ADVERSE EVENTS REPORTING

Adverse events (AE) or serious adverse events (SAE) reported by the patient or observed by the Investigator will be listed individually on an adverse event form in the CRF. The signs and symptoms, time of onset, duration, treatment (if any), and follow-up procedures (if any) will be reported, and the criteria for assessing causality to study drug and outcome categories should be defined.

Pre-existing conditions or illnesses which are expected to exacerbate or worsen are not considered adverse events and will be accounted for in the patient's medical history.

All adverse events are to be followed up for 30 days following the end of study or until resolution (whichever is sooner).

In order to classify AEs and diseases, preferred terms will be assigned by the Sponsor to the original terms entered on the eCRF using the Medical Dictionary for Regulatory Activities (MedDRA).

14.1 DEFINITIONS

14.1.1 AE

AE is any un-anticipated or unintended medical occurrence or worsening of a sign or symptom (including an abnormal laboratory finding) or disease in a study participant, which does not necessarily have a causal relationship with the study condition, procedures or study agent(s) that occurs after the informed consent is obtained.

14.1.2 SAE

An SAE is defined as any untoward medical occurrence that results in death, is immediately life-threatening, requires at least a 24-hour in-patient hospitalization or prolongation of existing hospitalization, results in persistent or significant disability/incapacity, or is a congenital anomaly/birth defect.

The definition of SAE also includes any important medical event. Medical and scientific judgment should be exercised in deciding whether expedited reporting is appropriate in other situations, such as important medical events that may not be immediately life-threatening or result in death or hospitalization but may jeopardize the patient or may require intervention to prevent one of the other outcomes listed in the previous definition. These should also usually be considered serious. Examples of such events are intensive treatment in an emergency room or at home for allergic bronchospasm; blood dyscrasias or convulsions that do not result in hospitalization; or development of drug dependency or drug abuse. Progression of malignancy (including fatal outcomes), if documented by the use of an appropriate method (for example, as per RECIST 1.1 criteria for solid tumours), should not be reported as an SAE and must be approved by the Sponsor.

Treatment within or admission to the following facilities does not meet the criteria of “in-patient hospitalization” (although if any other SAE criteria are met, the event must still be treated as an SAE and immediately reported):

- Emergency Department or Emergency Room
- Outpatient or same-day surgery units
- Observation or short-stay unit
- Rehabilitation facility
- Hospice or skilled nursing facility
- Nursing homes, custodial care or respite care facility

Hospitalization during the trial for a pre-planned surgical or medical procedure (one which was planned prior to entry in the trial), does not require reporting as a SAE to the Medical Monitor and Sponsor.

The definition of “related” is that there is a reasonable possibility that the drug caused any of the adverse events described in Table 2.

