8.2 INCLUSION CRITERIA

Patients must fulfil all of the following inclusion criteria to be eligible to enrol into the study:

1. Provision of informed consent.
2. ≥ 18 years of age.
3. Histologically confirmed prostate cancer and/or PSA of > 100 ng/mL at original diagnosis
4. Metastatic disease evidenced by either CT/MRI imaging or bone scan.
5. Objective evidence of disease progression as defined by either:
 - i. Radiographic progression of in nodal or visceral metastases and bone disease progression with 2 or more new lesions
 - ii. Rising PSA value ≥ 2 ng/ml in at least 3 measurements, at least 1 week apart, with castrate levels of serum testosterone.
6. Eligible to receive palliative radiation therapy to at least one symptomatic lesion for management of disease.
7. ECOG Performance status 0-2.
8. A minimum life expectancy of 24 weeks.
9. Adequate bone marrow, hepatic and renal function as evidenced by:
 - Absolute neutrophil count (ANC) $> 1.5 \times 10^9$ /L
 - Platelet count $> 100 \times 10^9$ /L
 - Hemoglobin > 9.0 g/dL
 - Serum bilirubin $< 1.5 \times$ ULN
 - AST/ALT (SGOT/SGPT) $< 2.5 \times$ ULN for the reference laboratory or $< 5 \times$ ULN in the presence of liver metastases
 - Serum creatinine $< 1.5 \times$ ULN
10. Ongoing androgen deprivation therapy with luteinizing hormone-releasing hormone (LHRH) agonist or antagonist.
11. At least 4 weeks must have elapsed prior to commencement of NOX66 treatment since prior chemotherapy, investigational drug or biologic therapy and any toxicity associated with these treatments has recovered to \leq NCI-CTCAE (version 4.03) Grade 1.
12. At least 21 days must have elapsed following major surgery and any surgical incision should be completely healed.

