12.2 STATISTICAL METHODOLOGY

This section describes the planned statistical analyses in general terms. A complete description of the statistical analysis will be specified in a statistical Analysis Plan (SAP) finalised prior to completion of the study.

General: Data will be summarized by using counts and percents for discrete parameters, and by descriptive statistics (e.g. number of observations, mean, standard deviation, median, minimum and maximum) for continuous parameters. Subject disposition and baseline characteristics will be presented for all treated patients. Data will be analysed as collected. No imputation of values for missing data will be performed. Standard clinical monitoring and data management practices will be used to ensure the integrity of the data.

Populations for analysis: There will be two study populations defined for this study. The safety population will consist of all patients who received at least one dose of NOX66. This population will be used in all safety summaries. The efficacy population will consist of all patients who complete radiation therapy with at least 7 days of NOX66 dosing.

Baseline Comparisons and Patient Disposition: Demographic and baseline disease characteristic data summarisation will be performed in order to descriptively document any safety and efficacy findings. Data to be tabulated will include demographic features such as age and race, as well as medical history. The number and percentage of patients who complete the study or who withdraw for any reason will be presented.

Efficacy Analysis: Results from (i) RECIST 1.1 response assessment for target lesions and non-target lesions, (ii) ECOG Performance Score and (iii) Pain scores. Changes from baseline in levels of serum PSA levels will be listed.

Overall and progression-free survival, PSA and pain scores collected during the extended follow-up period will be summarized in the same manner as for the immediate post-treatment follow-up period.

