Safety Analysis: The safety will be assessed through the analysis of the reported incidence of treatment emergent AEs, including SAEs, dose-limiting toxicities, AEs leading to withdrawal, events of at least CTCAE Version 4.03 Grade 3 in severity, and AEs related to study treatment. Treatment emergent AEs are those with an onset on or after the initiation of therapy. Other safety endpoints include laboratory results, physical examinations, vital signs, and changes in ECOG status. A copy of CTCAE Version 4.03 scoring system may be downloaded from:

http://evs.nci.nih.gov/ftp1/CTCAE/CTCAE_4.03_2010-06-14_QuickReference_8.5x11.pdf.

The adverse events will be summarized by MedDRA coding terms, System Organ Class (SOC), and preferred term for all treated patients and by dose cohort. The AEs will also be tabulated by maximum severity and maximum relationship to study drug where applicable. The number and percent of patients experiencing dose-limiting toxicities will be summarized by dose cohort, by DLT, and system organ class for all treated patients. Other safety endpoints, which include change from baseline in laboratory results and vital signs, and shifts in physical examinations, will be summarized throughout the study by visit for each dose level for all treated patients.

Concomitant medications: are to be listed for all patients.

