14.2 RESPONSIBILITIES FOR REPORTING

Investigators and the Sponsor are required by regulatory agencies worldwide to report adverse events which involve patients being administered a pharmaceutical product.

All serious adverse events (SAE) occurring from the signing of informed consent until 30 calendar days after last study visit whether related to drug or not, must be reported to the Medical Monitor and appropriate Sponsor contact person within 24 hours of first knowledge of the experience using the appropriate study SAE Report Form. SAEs are to be followed until resolution or stabilisation (with autopsy report if applicable).

Although pregnancy is not a formal SAE, if the study participant or the partner of a study participant becomes pregnant while the study participant is on study, the pregnancy is to be reported on the pregnancy report form via the SAE process.

Deaths and other SAEs occurring > 30 calendar days after last study visit that are deemed 'possibly' or 'probably' related to the study treatment must be reported as SAEs on the SAE Report Form within 1 day of first knowledge of the event by the treating physician or research personnel (with an autopsy report if available).

Deaths occurring > 30 calendar days after last study visit and not attributed to study treatment (e.g., disease progression) need not be reported as SAEs, but simply captured on the appropriate CRF.

The investigative sites will send the SAE report to the Sponsor's Medical Monitor via fax or e-mail and to the Sponsor's pharmacovigilance manager using the contact information below.

Primary Contact [name] [name]	[contact] Email: [contact]
Alternate Contact Study Manager: [name]	Tel: [name]; Fax: [name] Email: [contact]
Pharmacovigilance (DATAPHARM Australia) Manager: [name]	[contact]; [contact] Email: [contact]

Transmission of the SAE Report Form should be confirmed by the site personnel submitting the report. The first report must contain as minimum the study ID, patient number, a description of the event, the name of the investigational product, estimate of causality and the name of the person reporting the event.

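### A progression death can be left out of both the safety and the survival summaries: no all-cause death table is planned, and the analysis set for OS and PFS is not named

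*Combined protocol and SAP*

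**What the plan says.** **Reporting rules.** Section 14.1.2 says that "Progression of malignancy (including fatal outcomes), if documented by the use of an appropriate method" "should not be reported as an SAE and must be approved by the Sponsor". RECIST 1.1 is given only as an example of a method, and no time limit is set. The opening of section 14 adds that "Pre-existing conditions or illnesses which are expected to exacerbate or worsen are not considered adverse events". Section 14.2 requires SAEs to be reported, related or not, from consent to 30 days after the last study visit. For deaths after that point, it says that those "not attributed to study treatment (e.g., disease progression) need not be reported as SAEs".

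**Safety analysis.** Section 12.2 bases it on "treatment emergent AEs, including SAEs, dose-limiting toxicities, AEs leading to withdrawal, events of at least CTCAE Version 4.03 Grade 3 in severity" and related AEs, with laboratory, examination, vital-sign and ECOG data besides. The safety population is everyone who took at least one dose. No summary of deaths is named there, nor among the primary outcome measures in section 10.1.

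**Survival.** OS and PFS come under the Efficacy Analysis paragraph of section 12.2, with no analysis set stated. Only one other population is defined: "The efficacy population will consist of all patients who complete radiation therapy with at least 7 days of NOX66 dosing". Section 10.1 counts survival from the start of study treatment, and section 7 follows all patients for survival. Section 8.5 lets the Sponsor replace patients who are not evaluable for efficacy.

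**The concern.** The primary objective is the safety of NOX66 with radiotherapy in end-stage patients, with no control arm. Whether an early death is due to disease or to treatment is a hard judgement in this setting. As the plan is written, a judgement of disease progression can decide whether the death appears in the safety summaries at all. The death may not be an SAE (section 14.1.2), it may not be an AE (section 14), and no table of deaths would catch it otherwise.

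Survival would normally be the backstop. If OS is run in the efficacy set, however, it is conditioned on completing treatment, and the earliest deaths are the ones that drop out. Section 8.5 then allows the patient to be replaced. The dose-escalation rule in section 10.2.14 counts only discontinuations for NOX66-related AEs, so a death attributed to progression does not enter it either. With cohorts of four, one such death is a large share of what is known about a dose.

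**Working it through.** **1. The plan's own figure.** 3 cohorts × 4 + 12 in the expansion cohort = 24. This reproduces. No alpha, power or mortality rate is stated, so there is no other figure to check.

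**2. Reporting rules side by side, for a death put down to documented progression inside the reporting window.**
- Section 14.1.2: not an SAE, whenever it occurs.
- Section 14.2: progression deaths are exempted only beyond 30 days after the last study visit, which implies that earlier ones are reported.
- Section 14, opening: expected worsening of an existing condition is not an AE. Section 14.1.1, however, includes worsening of disease in the AE definition.

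Two sites could therefore handle the same death differently, each with a section to cite.

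**3. When death alone keeps a patient out of the efficacy set.**
- Radiotherapy starts on Day 2 (section 10.2.3) and takes five to eight days (section 9.3). Last day = 2 + 5 − 1 = Day 6, up to 2 + 8 − 1 = Day 9.
- Seven days of uninterrupted NOX66 from Day 1 are reached on Day 7.
- Entry to the set = max(last radiotherapy day, Day 7) = Day 7 to Day 9.

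Death by itself excludes a patient only up to about Day 7–9. A patient who stops radiotherapy early and dies later is also excluded, with no upper limit on the day of death.

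**4. What one excluded death does (exact 95% intervals).**

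| | All treated | Efficacy set |
|---|---|---|
| Whole study | 1/24 = 4.2% (0.1–21.1%) | 0/23 (upper limit 14.8%) |
| One cohort of four | 1/4 = 25% (0.6–80.6%) | 0/3 (upper limit 70.8%) |

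If the patient is replaced and 25 are treated, the contrast is 1/25 = 4.0% against 0/24.

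**5. Effect on Week 24 survival.** Let D be total deaths by Week 24 and k the number excluded. All treated: 1 − D/24. Efficacy set: 1 − (D − k)/(24 − k). The values of D and k are assumed.

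| D | All treated | k = 1 | k = 2 |
|---|---|---|---|
| 3 | 87.5% | 91.3% | 95.5% |
| 6 | 75.0% | 78.3% | 81.8% |
| 9 | 62.5% | 65.2% | 68.2% |

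**6. How likely a death by Day 9 is.** The documents do not say. Assume exponential survival with a median of m months: p = 1 − exp(−ln 2 × 9/(30.44 m)).
- m = 6: p = 3.36%; 24p = 0.81 expected deaths; 1 − (1 − p)^24 = 56% chance of at least one.
- m = 24: p = 0.85%; 24p = 0.20; chance 18.5%.

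The 24-week life-expectancy criterion (section 8.2) should make such deaths rarer than this.

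**The case against.** The strongest reply is that nothing in the text assigns OS to the efficacy set. Survival runs from treatment start, all patients are followed, and section 8.4 continues follow-up after withdrawal. Section 12.2 also describes the analyses only in general terms and defers detail to a SAP, which may settle both the set and a death table. This stands in part: the defect is an unnamed set, not a stated exclusion. But the only set defined for efficacy depends on completing treatment, and the safety set is tied to safety summaries, so the natural default is the wrong one.

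Sections 14.1.2 and 14.2 can also be read together, one defining an SAE and the other setting the window for reporting it. That is possible, and it is why the conflict is one of implication only.

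Stronger readings are tempting but not supported:
- **That the death would show only as a withdrawal.** The synopsis (Statistical methods) lists AEs and outcomes per patient, so it should appear there too. Neither place is a safety or survival summary, and section 12.2 does not require withdrawals to be tabulated by reason.
- **That the progression which made the patient eligible could serve as the documentation.** No section allows this. The RECIST definitions in section 10.4.8 judge progression against measurements since treatment started, new lesions, or unequivocal worsening of existing ones.
- **That every death on study could move out of the SAE count.** Only deaths with documented, Sponsor-approved progression could.

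The overlap of the two gaps is also narrow. The first scheduled scan is at Week 6, so a death by Day 9 would need unscheduled documentation to count as progression. The overlap is wider for patients who stop radiotherapy early and die later.

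**Conclusion.** The point holds as a gap in the planned summaries. A death attributed to progression can be kept out of the SAEs, and possibly the AEs, under rules that do not agree with each other. No all-cause death summary is planned to catch it. If the efficacy set is used for survival, a patient who dies or stops radiotherapy before qualifying is missing from OS as well.

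The size per patient is 1/24 against 0/23 overall, or 1/4 against 0/3 in a cohort. In the assumed scenarios, Week 24 survival is overstated by about 3 to 4 percentage points for one excluded death and 6 to 8 for two. These figures rest on OS being run in the efficacy set, which the text neither states nor rules out. How often it would happen cannot be derived from the documents. The missing death table and the conflict over reporting do not depend on that choice of set.

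**What to change.** - **Section 12.2, survival:** state that OS and PFS are analysed in all treated patients (the safety population) from the first dose, including anyone replaced under section 8.5.
- **Section 12.2, safety:** add a table and listing of deaths from any cause in the safety population by dose level, within 30 days of last study treatment and to Week 24. Show study day, attributed cause and relatedness, whatever the SAE status.
- **Section 13.2:** provide that listing to the Study Steering Committee.
- **Sections 14, 14.1.2 and 14.2:** reconcile them so that one rule covers how progression deaths inside the reporting window are reported.

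The cost is one table, one listing and some wording. Survival information is already collected for all patients. The reported safety profile may look slightly less favourable, but each death will be shown with its attribution.

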14.1.3 Guidelines for determining causality and severity

The criteria used for determining the relationship between the study drug/s and the Adverse Event are shown in Tables 2 and 3:

Table 2 Criteria for determining relationship between AE and idronoxil (NOX66)

Unlikely/unrelated:	An AE with a temporal relationship to drug administration, which makes a causal relationship improbable, and in which other drugs, chemicals or underlying disease provide plausible explanations.
Possible	An AE with a reasonable time sequence to administration of the drug, but which could also be explained by concurrent disease or other drugs or chemicals. Information on drug withdrawal may be lacking or unclear.
Likely	An AE with a reasonable time sequence to administration of the drug, unlikely to be attributed to concurrent disease or other drugs or chemicals, and which follows a clinically reasonable response on withdrawal (rechallenge). Rechallenge information is not required to fulfil this definition
Certain	An AE occurring in a plausible time relationship to drug administration and cannot be explained by concurrent disease or other drugs or chemicals. The response to withdrawal of the drugs should be clinically plausible. The event must be definitive pharmacologically or phenomenologically using a satisfactory rechallenge procedure if necessary and feasible

Table 3. Adverse event outcome categories

Resolved'	The patient has fully recovered from the adverse event with no residual effects observable.
'Resolved with Sequelae'	The patient has recovered from the adverse event, however there are residual effects observable.
'Ongoing'	The adverse event is still present and observable.
'Death'	The patient died as a result of the adverse event.
'Unknown'	The outcome of the adverse is unknown at the time of report.

14.2 RESPONSIBILITIES FOR REPORTING

Investigators and the Sponsor are required by regulatory agencies worldwide to report adverse events which involve patients being administered a pharmaceutical product.

All serious adverse events (SAE) occurring from the signing of informed consent until 30 calendar days after last study visit whether related to drug or not, must be reported to the Medical Monitor and appropriate Sponsor contact person within 24 hours of first knowledge of the experience using the appropriate study SAE Report Form. SAEs are to be followed until resolution or stabilisation (with autopsy report if applicable).

Although pregnancy is not a formal SAE, if the study participant or the partner of a study participant becomes pregnant while the study participant is on study, the pregnancy is to be reported on the pregnancy report form via the SAE process.

Deaths and other SAEs occurring > 30 calendar days after last study visit that are deemed 'possibly' or 'probably' related to the study treatment must be reported as SAEs on the SAE Report Form within 1 day of first knowledge of the event by the treating physician or research personnel (with an autopsy report if available).

Deaths occurring > 30 calendar days after last study visit and not attributed to study treatment (e.g., disease progression) need not be reported as SAEs, but simply captured on the appropriate CRF.

The investigative sites will send the SAE report to the Sponsor's Medical Monitor via fax or e-mail and to the Sponsor's pharmacovigilance manager using the contact information below.

Primary Contact [name] [name]	[contact] Email: [contact]
Alternate Contact Study Manager: [name]	Tel: [name]; Fax: [name] Email: [contact]
Pharmacovigilance (DATAPHARM Australia) Manager: [name]	[contact]; [contact] Email: [contact]

Transmission of the SAE Report Form should be confirmed by the site personnel submitting the report. The first report must contain as minimum the study ID, patient number, a description of the event, the name of the investigational product, estimate of causality and the name of the person reporting the event.

